5 JUSTIFICATION FOR THE DESIGN OF THE CLINICAL INVESTIGATION

5.1 Pre-clinical data

No pre-clinical data are available for the Renamic Neo programmer, software or PK-222-L cable. Animal tests were not performed for the Renamic Neo programmer as it is an external device. The most relevant verification and validation tests for the Renamic Neo system are described in the Investigator's Brochure⁷. Investigational devices will not be provided to study sites until all tests are successfully completed.

5.2 Clinical data

For the Renamic Neo system, no clinical data are available yet.

The preceding programmer Renamic has been used in many BIOTRONIK sponsored clinical studies, e.g.

- QP ExCELS (NCT03155724)⁸
- Eluna Family Sentus BP Master Study (NCT02059629)⁹
- Matrix (NCT01774357)¹⁰
- BIO|MASTER.Ilivia / Plexa Family (NCT02774616)¹¹
- BIO|MASTER.BioMonitor 2 (NCT02565238)¹²

Renamic was granted CE approval in Sep 2010 and was predominantly used in any BIOTRONIK study starting from January 2015 onwards that supported regulatory approval. Renamic was not explicitly investigated in these studies, but the positive results of these studies imply a correct and safe functioning of this programmer generation. As the functioning of the Renamic Neo is highly similar to that of the Renamic it is expected that the complication rate will be very low.

5.3 Justification

The main objective of this study is to provide evidence for the clinical safety, performance and usability of the Renamic Neo programming device including software and PK-222-L ECG cable.

The study is designed in a use case centric approach, i.e. it follows the usage of Renamic Neo programmer system and not the individual patients, so that a sufficient number of use cases is collected that allows for the detection of possible adverse device effects and device deficiencies caused by the programmer.

Patients will stay in the study only for implantation and PHD or follow-up and are terminated directly afterwards as ADEs and DDs related to the programmer are expected to occur only during the use of the programmer.

As the Renamic Neo system will be used for the first time in clinical routine, a significant number of use cases from implantation – given that the PSA module might be used – and follow-ups shall be included in this study. Please refer to section 11 for the justification of the sample size calculation.

Approximately 10 clinics with 2-3 Renamic Neo systems each are planned to participate. The multi-centric design will ensure that different environments in which the programmer is placed and used as well as potential hospital specific differences in programmer handling and usage are covered. While just several sites would be sufficient for that purpose, approximately 10 sites will be involved in order to realize a fast study completion. Depending on the special requirements of the sites to use the programmer at different locations at the same time, sites will receive 2-3 Renamic Neo device systems respectively. This results in an approximate number of 20-30 investigational devices.

To cover a broad range of programmer functionalities the device will be used during implantations including PSA usage, if applicable, and follow-up visits. Furthermore, the

enrollment of patients will not be restricted to any subgroup or indication in order to cover use cases for the different CRM devices.

The endpoints adverse device effects and device deficiencies are selected to analyze the safety of the Renamic Neo system and to identify possible residual risks of the programmer. Based on rare observations of events caused by the programming device in the past, only a small number of events are expected. Therefore, no power calculation and no hypothesis for the event-free rate can be provided.

Additional data from implantation and follow-up visits will be collected to confirm the performance and usability of the Renamic Neo system.

6 RISKS AND BENEFITS OF THE DEVICE AND CLINICAL INVESTIGATION

6.1 Anticipated clinical benefits

The Renamic Neo device is a state of the art programming device that is designed to integrate into the clinical workflow in order to make the clinical routine more efficient. Apart from this potentially better workflow there will be no benefit for patients that participate in this clinical study.

6.2 Anticipated risks

6.2.1 Anticipated adverse device effects

Adverse device effects anticipated for the use of the Renamic Neo system are described in section 18.7. Since no additional procedures outside the clinical routine are required in this study, no further study-specific adverse device effects (ADEs) are anticipated.

6.2.2 Residual risks associated with the device

In principle, technical failures in the programmer due to transmission errors, random component failures, software malfunction, or other events that could lead to harm, cannot be ruled out completely. These are expected but unlikely events.

Instructions for use to support correct use and to avoid use error are provided, but user errors cannot be prevented completely. Potential harm related to technical failure of the programmer or use errors have been evaluated¹³ and are listed below:

- Nausea / sickness / slight dizziness
- Cardiac arrest and tachycardia
- Prolonged undesired medical condition, anesthesia or psychological stress
- Acute and serious heart failure
- Thermal tissue load
- Misdiagnosis and repeated invasive intervention
- Infection
- Asystole

There may be other risks associated with the devices that are currently unforeseeable.

6.2.3 Risk associated with participation in the study

Unauthorized access to the patient data or inadequate data protection (e.g. submission of non-pseudonymized data to the sponsor representatives) are possible risks associated with the participation. BIOTRONIK undertakes technical and organizational measures to protect patient's data privacy and adheres to applicable European data protection laws.

There are no study-related procedures outside the clinical routine care planned. PSA measurement procedures do not differ from the procedure with the predecessor Renamic PSA module. Therefore, no additional risks or burdens are expected to derive from participating in the study.

6.2.4 Possible interactions with concomitant medical treatments

The use of the Renamic Neo is not expected to interfere with concomitant medication or other medical treatment.

The individual cardiovascular medication may have to be adapted to the patient's needs independent of the Renamic Neo device.

6.3 Steps to control or mitigate the risks

Risks related to the design, the technical characteristics, and the handling of the Renamic Neo programmer as mentioned above and in section 18.7 have been reduced by appropriate risk control measures defined in the respective BIOTRONIK Function System Risk Analysis (FSR)¹³.

They are minimized through the compliance with the technical manual and special training of the clinical site staff on the Renamic Neo by BIOTRONIK staff, compliance with this clinical investigation plan and technical procedures, close monitoring of the patient's physiologic status during the use of the Renamic Neo, and by promptly supplying BIOTRONIK with all pertinent information required by this clinical investigation plan.

National data protections laws and the European Regulation (EU) 2016/679 must be followed. Non-pseudonymized data inadvertently sent to the sponsor will be handled upon discovery according to BIOTRONIK's internal processes to ensure that only pseudonymized documents are available at and used by the sponsor. Access to the clinical data management system (CDMS) is restricted by secured internet platforms using user IDs and passwords. Further details on the risk mitigation regarding the CDMS are outlined in the data management plan of the study. Access to investigational devices is restricted (see section 15) Nevertheless, a residual risk remains (see section 6.2.2).

6.4 Risk-to-benefit rationale

Patients participating in the BIO|CONCEPT.Renamic Neo study are scheduled for an implantation of an IPG, ICD, CRT device or ICM from BIOTRONIK or already have such a BIOTRONIK device implanted. Programming devices are essential to adapt the implants to the patient's needs and to obtain data about device function and physiologic data. By participating in this study patients have no direct benefits, but they contribute to the medical progress which may benefit other patients in the future. The advanced features and properties (e.g. internal battery, less weight) of the Renamic Neo system may improve the clinical workflow.

The use of programmers to interrogate, and program IPGs, ICDs, CRT-devices and ICMs is state-of-the-art. Programmer-related complications are rare. The risks of the use of Renamic Neo system do not exceed the levels expected and acknowledged for programmers, and are clearly outweighed by the possible benefits.

The Renamic Neo system therefore has a favorable benefit-risk profile - the benefit-risk profile according to current knowledge and the state-of-the-art in the affected medical areas and according to available medical alternatives is positive.

7 OBJECTIVES AND HYPOTHESES

7.1 Objectives

This study is designed as a pre-market clinical study to provide evidence on the safety, performance and usability of the Renamic Neo programmer hardware, software and ECG cable PK-222-L to support regulatory approval, with a focus on requirements of the European Medical Device Regulation (MDR). The study is also intended to identify and evaluate residual risks associated with the use of the Renamic Neo programmer system that remained unrevealed even after risk analysis, risk mitigation and completed validation of the device. The results will be used to update the clinical evaluation of the devices.

7.2 Endpoints and hypotheses

7.2.1 Primary endpoint and hypotheses

There is no pre-specified statistical hypothesis and thus no primary endpoint. All analyses are explorative only.

7.2.2 Endpoints

In this study the number of adverse device effects and device deficiencies (DD) that occur in patients, users or other persons will be evaluated. Definitions are given in section 18. The investigator is asked to report any ADEs or DD that occurred during implantations and follow-ups.

- Number of adverse device Effects / device deficiencies per number of implantations
- Number of adverse device Effects / device deficiencies and per number of follow-up cases

ADEs will be adjudicated by an internal adjudication board, whereby the seriousness and device relatedness will be re-examined. If any amply documented external physical influence (e.g. accident, general power blackout) or medical AE caused the ADE, it does not contribute to this endpoint.

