8.1.4 Methods

All clinical procedures in this study will be performed according to clinical routine. Detailed information on the use of the Renamic Neo system can be found in the Technical Manuals and other study documents. The time schedule and all parameter and measurements that are recorded during the study are described in section 9.1. The corresponding data will be documented in the respective CRFs at the following points in time:

For patients who are scheduled for a BIOTRONIK active device implantation	For patients who are already implanted with a BIOTRONIK active device:

 • Enrollment/ baseline • Implantation • Pre-hospital discharge • Termination 	
 • Enrollment/ baseline • Follow-up • Termination

The following events shall be documented at any time

- Adverse events (including device related adverse events in users and other persons)
- Device deficiencies

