8.1.6 Replacement of subjects

Patients are enrolled in the study only for the time of study related measurements during implantation and PHD or follow-up. Patients that drop out before any study related use of the Renamic Neo system will be replaced. No drop-out rate was defined (see section 11.4).

8.2 **Used devices and comparators**

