## 7. Analysis Sets & Subgroups

### 7.1. Analysis Sets

Data file, identifier patient display id full enrollment	Variable name	Variable label	Variable level	Nominal values
enrollment	DMSUBSPS	Patient signed the informed consent personally	nominal	 Yes  No
enrollment	DMRPRSPS	An independent witness signed the informed consent since the patient is unable to write	nominal	 Yes  No
study termination	DSDRPPRO	Please specify Drop-out according to protocol	nominal	 No implantation of an active implantable BIOTRONIK device  Other

Data file, identifier patient display id full & autom SVTYP	Variable name	Variable label	Variable level	Nominal values
general assessments	autom SVTYP	Visit type	nominal	 Implantation  Pre-hospital discharge follow-up (PHD)  Regular follow-up after PHD
	PRSVPRG	Was the Renamic Neo programmer used for the visit	nominal	 Yes  No

Data file, identifier patient display id full	Variable name	Variable label	Variable level	Nominal values
data SAR	analysis set enr SAR 	Enrollment analysis set (patients with Biotronik device and usage of Renamic Neo)	nominal	 Yes  No
data SAR	analysis set imp SAR 	Implantation analysis set (patients with Biotronik device and usage of Renamic Neo during implantation)	nominal	 Yes  No
data SAR	analysis set PHD FUP SAR 	PHD and regular FU analysis set (patients with Biotronik device and usage of Renamic Neo during PHD or FU)	nominal	 Yes  No

The implantation analysis set and the PHD/FUP analysis set are not mutually exclusive, i.e. specific patients can belong to both analysis sets.

 IF (DMSUBSPS = Yes OR DMRPRSPS = Yes) AND date enr SAR not missing AND  
 TIINC01 type ≠ No implantation of an active implantable BIOTRONIK device AND  
 any general assessments per patient with PRSVPRG = Yes  
 THEN analysis set enr SAR = Yes  
 ELSE analysis set enr SAR = No

 IF analysis set enr SAR = Yes AND  
 any general assessments per patient with (PRSVPRG = Yes AND autom SVTYP per patient = Implantation)  
 THEN analysis set imp SAR = Yes  
 ELSE analysis set imp SAR = No

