### 10.1. Analysis Set and Data Selection

All analyses are performed for patients in the implantation analysis set using a specific data selection before / at implantation.

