data SAR	descriptive	n sade SAR 	Number of any Serious Adverse Device Effects based on internal adjudication	metric to be reported as nominal	o 1 o 2 ...
data SAR	descriptive	n dd SAR 	Number of any Device Deficiencies based on internal adjudication	metric to be reported as nominal	o 1 o 2 ...
data SAR	descriptive	n ade dd SAR 	Number of any Adverse Device Effects (serious or non-serious) and Device Deficiencies based on internal adjudication	metric to be reported as nominal	o 1 o 2 ...

 If specific patient with AERELSET = Yes AND AESER = No  
 THEN any ade SAR = Yes  
 ELSE any ade SAR = No

 If specific patient with AERELSET = Yes AND AESER = Yes  
 THEN any sade SAR = Yes  
 ELSE any sade SAR = No

 If specific patient with DEADED = Yes  
 THEN any dd SAR = Yes  
 ELSE any dd SAR = No

 If specific patient with AERELSET = Yes OR DEADED = Yes  
 THEN any ade dd AERELSET SAR = Yes  
 ELSE any ade dd SAR = No

 Count number of events per patient with AERELSET = Yes AND AESER = No

 Count number of events per patient with AERELSET = Yes AND AESER = Yes

 Count number of events per patient with DEADED = Yes

 Count number of events per patient with AERELSET = Yes OR DEADED = Yes

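### SAP chapters 10 and 11 report endpoint events only for patients with PRSVPRG = Yes at that visit type, so an event at a visit where the programmer could not be used can be missing from both

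*Protocol*

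**What the plan says.** Protocol 7.2.2 (Endpoints) sets the scope: the "number of adverse device effects and device deficiencies (DD) that occur in patients, users or other persons will be evaluated". It adds that "The investigator is asked to report any ADEs or DD that occurred during implantations and follow-ups", and it expresses the result as "Number of adverse device Effects / device deficiencies per number of implantations", with a parallel rate for follow-up cases.

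The SAP repeats this endpoint at the head of chapters 10 and 11, but carries it out through patient-level sets:

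- **Enrollment set (SAP 7.1, footnote 2).** Besides consent and device conditions, it requires "any general assessments per patient with PRSVPRG = Yes". PRSVPRG is a per-visit yes/no item asking whether the Renamic Neo was used.
- **Implantation set and PHD/FU set (footnotes 3 and 4).** These require PRSVPRG = Yes at a visit of that type.
- **Chapter 10.** "All analyses are performed for patients in the implantation analysis set". Footnote 15 adds that the adjudicated use case, PRUCASE, must be the implantation value (labelled 'Implementation' in the SAP).
- **Chapter 11.** The same outputs are repeated for the PHD/FU set, with PRUCASE = PHD / Follow-up (footnote 24).
- **Variables.** They are yes/no flags per patient or counts per patient. The combined count in footnote 23 reads "Count number of events per patient with AERELSET = Yes OR DEADED = Yes".

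SAP 5.9 lists the adverse event, internal adjudication and device deficiency datasets among those to be analyzed. The endpoint chapters draw only on the adjudication dataset.

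**The concern.** The protocol describes a use-case-centred design (5.3) whose purpose includes finding residual risks that earlier validation missed (7.1). A deficiency severe enough to stop the programmer being used is an obvious example. The SAP makes reporting of an event conditional on the programmer having been used at the visit where the event occurred, so the reporting condition can depend on the event itself. An event that fails the condition leaves both the count and the case listing. Its visit leaves the denominator too. Protocol 5.3 expects only a small number of events, so a single unreported one could matter to how the result reads.

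**Working it through.** **1. The SAP rules applied literally.** Inputs are footnotes 2 to 4 (sets), 15 and 24 (data selection) and 18 and 22 (deficiency flag and count). Each row is a deficiency that adjudication marked as endpoint-relevant (DEADED = Yes) and that is linked to a patient.

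| Situation | PRSVPRG by visit | PRUCASE | In implantation set | In PHD/FU set | Chapter 10 | Chapter 11 |
|---|---|---|---|---|---|---|
| Deficiency at implantation, Neo still used | Implantation Yes, PHD Yes | Implantation | yes | yes | reported | no |
| Use prevented at implantation, Neo used at PHD | Implantation No, PHD Yes | Implantation | no | yes | **no** | **no** |
| Use prevented at implantation, Neo not used at PHD | Implantation No, PHD No | Implantation | no | no | **no** | **no** |
| Use prevented at PHD, Neo used at implantation | Implantation Yes, PHD No | PHD / Follow-up | yes | no | **no** | **no** |
| Use prevented at a follow-up-only visit | FU No | PHD / Follow-up | no | no | **no** | **no** |

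The second row shows the gap most clearly. The patient is in the study and in one analysis set. Chapter 10 rejects the event because the patient is not in the implantation set. Chapter 11 rejects it because PRUCASE is the implantation value.

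**2. Search for a safeguard.** SAP 10.4 says nothing is excluded, but only from the analysis set already specified. Protocol 11.5 promises that any potential ADE or DD will be analyzed and discussed, but the SAP defines no output for events outside the sets. No SAP chapter reports the adverse event or device deficiency dataset directly.

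**3. The plan's own detection figures.** Protocol 11.2.1 and 11.2.2 assume a problem with 5% probability per use case. With X ~ Binomial(n, 0.05), P(X ≥ r) for r = 1, 2, 3 is:

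- n = 50: 92.3 / 72.1 / 45.9% (stated 92 / 72 / 46%). For r = 1 this is 1 − 0.95^50.
- n = 100: 99.4 / 96.3 / 88.2% (stated 99 / 96 / 88%).

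All six figures reproduce.

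**4. Illustration if a share f of events goes unreported.** The documents give no f, so this is an assumption shown over a range. Replace 0.05 by 0.05 × (1 − f):

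| f | n = 50, at least 1 / 2 / 3 | n = 100, at least 1 / 2 / 3 |
|---|---|---|
| 10% | 90.0 / 66.4 / 39.2% | 99.0 / 94.3 / 83.3% |
| 20% | 87.0 / 60.0 / 32.3% | 98.3 / 91.3 / 76.8% |
| 40% | 78.2 / 44.5 / 18.9% | 95.2 / 80.5 / 58.0% |

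**5. Effect of one event.** 1/50 = 2.0%, exact 95% CI 0.05 to 10.6%. If that visit leaves numerator and denominator, the result is 0/49, with exact upper limit 1 − 0.025^(1/49) = 7.3%. If 50 visits with use are still reached, it is 0/50, with upper limit 1 − 0.025^(1/50) = 7.1%.

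**The case against.** The best counter-argument is that loss needs several things at once: the programmer fails completely, no second Renamic Neo is used, and the site answers No. Sites hold 2 to 3 systems (protocol 5.3). Protocol 18.2.1 foresees replacing the programmer after a failed interrogation, and SAP 15.1 counts several programmers per patient. If a second Renamic Neo is used, PRSVPRG is Yes and the event is reported. Several form items also treat a failed function as use without success, so a site might well answer Yes. All of this stands and limits how often the gap would bite. It does not close the gap, because the SAP never says whether an attempt counts as use.

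Impact is also limited. There is no hypothesis, primary endpoint or pass/fail criterion (protocol 7.2.1, 11.5), and protocol 11.2 places the value in discussing event types and circumstances. Deficiencies must still be documented and sent to the sponsor (protocol 18.3, 18.8.1), so an event missing from chapters 10 and 11 is not unknown. The intervals for 1/50 and 0/50 overlap heavily.

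Four stronger readings are tempting, but the documents do not support them:

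- **Events in users or other persons are lost.** Such an event is reported if its record carries the ID of a patient in the set. The SAP does not describe the linkage, so loss is possible but not shown.
- **Affected patients are replaced.** Protocol 8.1.6 says "Patients that drop out before any study related use of the Renamic Neo system will be replaced", but programmer failure is not among the drop-out reasons in 8.3.5.
- **No total over use cases can be obtained.** Patients are enrolled once, for implantation plus PHD or for one follow-up (protocol 9.1). Within each set a patient is therefore one use case, and the total follows from the per-patient count distribution.
- **Deficiencies outside any use case belong in the rate.** Protocol 7.2.2 asks for events during implantations and follow-ups, so these are arguably beyond the endpoint.

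**Conclusion.** The point holds in a limited form. As written, the SAP can leave an adjudicated, endpoint-relevant event out of every endpoint count and listing when it occurs at a visit with PRSVPRG = No, although protocol 7.2.2 counts ADEs and DDs during implantations and follow-ups without that condition. The number of reported events can only fall as a result. The direction for the rate is less certain, because event-free visits without use also leave the denominator.

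The frequency is not given and may be nil. The conclusion assumes that a site may answer No after a failed attempt and that no other Renamic Neo is used at that visit. For scale, one lost implantation event changes 2.0% to zero. The sample size figures are correct and need no change.

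**What to change.** 1. In SAP 10 and 11, add an event-level listing and total of all adjudicated events with AERELSET = Yes or DEADED = Yes, by record id and PRUCASE, regardless of analysis-set membership. Reconcile it with the adverse event and device deficiency datasets.
2. Show any event not linked to a patient or a use case on a separate line, outside the rate.
3. State in SAP 7.1 and in the CRF guidance that an attempted use counts as PRSVPRG = Yes for every visit, with or without an event, so that numerator and denominator follow one rule.
4. If event-free attempts cannot be identified, report the out-of-set events as a count beside the rate. Adding only the visits with an event to the denominator would make it depend on the outcome.
5. Split by affected person only if that field is recorded. The adjudication variables listed in SAP 10.2 do not include one.

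The cost is SAP wording and one table from datasets already listed in SAP 5.9, plus queries for visits with PRSVPRG = No where the reason is unclear. Protocol 11.8 allows the SAP to be updated before database freeze or closure. The reported result may become slightly less favourable.
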